1.3 Schema

The general study design is summarised in Figure 1.

Figure 1 - Study Flow Chart

V1	V2	R/V3	V4-V15	EOT/V16	V17, V18
Week	Week	Week	Week	Week	Week
-6	-5	0	4-48	52	58, 64
Enrolment	Run-in			Follow-up	
Scree	ening		·		

V: Visit, R: Randomization

2. INTRODUCTION

2.1 Study Rationale

2.2 Background

Chronic obstructive pulmonary disease (COPD) is a progressive disease and a significant cause of morbidity and mortality worldwide. In contrast to other chronic diseases, COPD is increasing in prevalence and is projected to be the third leading cause of death and disability worldwide by 2020 (Global Initiative for Chronic Obstructive Lung Disease [GOLD 2019]).

Acute exacerbations of COPD (AECOPD) are responsible for a large portion of the economic burden of COPD. In addition to a substantial economic burden, AECOPDs are also responsible for much of the morbidity and mortality from COPD. Patients with frequent AECOPD show associated increased airway inflammation and accelerated decline in lung function compared with patients with infrequent exacerbations (Donaldson et al 2002).

Thymic stromal lymphopoietin (TSLP) is an upstream pleiotropic cytokine which is released by airway epithelial cells in response to either allergens or non-specific stimuli such as viruses, bacteria, and cigarette smoke, all of which are known to be associated with COPD exacerbations (Ziegler et al 2013). In response to an allergen or non-specific stimuli, TSLP activates dendritic cells, which stimulate Type 2 helper T (Th2) cells to differentiate and produce the Type 2 cytokines interleukin (IL)-4, IL-5, and IL-13 (Watson and Gauvreau 2014). TSLP can also drive Th17 cell expansion through activation of dendritic cells, which will increase neutrophil recruitment (Ziegler et al 2013).

TSLP, along with the other epithelial "alarmins", IL-25 and IL-33, activates Type 2 innate lymphoid cells (ILC2) and other inflammatory cell (including mast cells, basophils, and macrophages), thus promoting T2 inflammation by up-regulating Type 2 cytokines in response to an epithelial insult (e.g., pollutants, microbes, cigarette smoke, bacterial and viral infections, mechanical injury, trauma and pro-inflammatory cytokines etc.) (Camelo et al 2017).

TSLP protein is released from COPD epithelium following toll-like receptor (TLR) viral (Calvern et al 2012) and pro-inflammatory cytokine stimulation (Kato et al 2007, Lee and Ziegler 2007). TSLP protein has been detected in nasal secretions from healthy subjects undergoing natural rhinovirus infection (Perez et al 2014) as well as in the bronchoalveolar lavage (BAL) fluid and sputum of non-exacerbating COPD subjects (Ying et al 2008), and sputum (Anzalone et al 2018). TSLP mRNA expression is seen in airway epithelial cells in patients with COPD (Ying et al 2008).

Tezepelumab is a fully human immunoglobulin G (IgG) monoclonal antibody (mAb) directed against TSLP. Tezepelumab binds to human TSLP and prevents its interaction with the TSLP receptor (TSLPR). The hypothesis for the mechanism of action of tezepelumab in COPD is two-fold. First, because TSLP is one of the earliest responses to airway damage caused by a range of stimuli, inhibition of TSLP is expected to prevent the acute response to epithelial damage and prevent COPD exacerbations. Secondly, given that TSLP is an upstream and pleiotropic cytokine, the blockade of TSLP is anticipated to have broad impact on the spectrum of acute and chronic airway inflammatory responses seen in COPD. Both effects are expected to reduce COPD exacerbations and improve COPD symptoms (Camelo et al 2017).

Thus, it is hypothesized that inhibition of upstream TSLP by tezepelumab will be effective in reducing airway inflammation in patients with COPD and reducing annualized COPD exacerbation rates. The purpose of the present study is to investigate the ability of tezepelumab versus placebo to enable reduction of the annualized COPD exacerbation rate in subjects with moderate to very severe COPD receiving standard maintenance therapy.

2.3 Benefit/Risk Assessment

COPD is a progressive disease which is characterized by exacerbations and health related quality of life loss (GOLD 2019). Despite being treated with double and triple inhaled therapy, many COPD patients continue to have exacerbations (Wedzicha et al 2013).

It has been shown that tezepelumab, as add-on therapy to standard-of-care (SoC), significantly reduces asthma exacerbations, including exacerbations associated with hospitalization or ER visit, and improves lung function, asthma control, and quality of life in patients with severe uncontrolled asthma. Moreover, clinical improvements were seen irrespective of patient phenotype or biomarker status (Corren et al 2017). In the same study, tezepelumab was shown to decrease blood eosinophil counts, FeNO, and IgE levels, suggesting that multiple pathways are being impacted by blocking TSLP.

No clinical data are available to show the effect of tezepelumab in COPD. However, efficacy and safety data obtained in asthma supports clinical development of tezepelumab in COPD.

Use of tezepelumab has been demonstrated to show an important benefit in asthma in a phase 2b and phase 3 study. Tezepelumab has been well tolerated with an acceptable safety profile and no safety signals in subjects with severe, uncontrolled asthma identified in the completed studies to date. No serious allergic reactions or anaphylactic reactions considered related to tezepelumab were reported in the Phase 3 program. To date there has been a low incidence of ADA and neutralising antibodies (nAb) reported with tezepelumab treatment in the Phase 2 or Phase 3 studies. Although TSLP suppression could theoretically have unanticipated immune-related side effects impairing host defense against certain infections, there is no clear preclinical or clinical evidence supporting such a role, and no safety concerns related to

serious infections, severe infections or helminth infections have been detected in the completed studies to date.

Risk mitigation measures for important potential risks will be in place during the conduct of this study (refer to Table 3), in conjunction with the performance of the AstraZeneca's routine pharmacovigilance activities.

A detailed assessment of the overall risk/benefit of tezepelumab in patients with COPD is given in the Investigator's Brochure.

Table 3 – Risk Assessment

Important potential Risk	Summary of data/rationale for risk	Mitigation strategy			
	Study intervention				
Serious infections are defined as infections fulfilling criteria for regulatory reporting	The mechanism of action of tezepelumab suggests potential inhibitory effects on immune responses mediated by Th2 cells, leading to the possibility of diminution of the host's protective response to infection. Although there is a theoretical risk of serious infections with tezepelumab treatment, there is no data to support this potential risk. There is also no evidence for causal relationship with tezepelumab.	Vulnerable participants will be excluded based on eligibility criteria, and randomised participants will be monitored by safety blood work throughout the study; and through standard AE/SAE reporting. Participants will be excluded if they received systemic immunosuppressive or immunomodulating drugs within 3 months prior to Visit 1; or if they have a history of a known immunodeficiency disorder; or have a history of clinically significant infection requiring treatment with systemic antibiotics or antiviral medications finalised < 2 weeks before Visit 1 or during the run-in period or at randomisation; or who have evidence of active coronavirus disease 2019 (COVID-19) infection during the run-in period; or have had tuberculosis requiring treatment. Serious infections are an AESI and			
		Serious infections are an AESI and participants who develop serious			

		infection will be followed up
N		closely throughout study.
Malignancies	Given the potential theoretical risk due to the mechanism of action of tezepelumab, the long-term treatment intended for a chronic disease and the nature of malignancy development, malignancy is included as an important potential risk. There is no evidence to suggest an increase in malignancies in the tezepelumab data to-date in either pre-clinical or clinical studies. No causal relationship with tezepelumab could be established for cases reported.	Participants with current malignancy or whose curative therapy was completed recently will be excluded from participation based on eligibility criteria. All participants will be closely followed during the study for any adverse events/serious adverse event, including malignancies that are considered AESI.
Serious cardiac events	A numerical imbalance in cardiac disorder SAEs was observed in the DESTINATION Long Term Extension study (see Investigator's Brochure) with more events in participants treated with tezepelumab versus participants treated with placebo. None of the cardiac disorder SAEs was considered causally related to tezepelumab by investigators or Independent Adjudication Committee. There is no known mechanism by which blocking TSLP would lead to cardiac pathophysiology.	Participants with cardiac disorders that are not stable in the opinion of the investigator or who present meaningful abnormal findings in examination, lab assessments or ECG will be excluded based on eligibility criteria. All participants will be closely followed during the study for any adverse events, including serious cardiac events that are considered AESI.
Potential risks	Summary of data/rationale	Mitigation strategy
i oteniam i iyin	for risk	iningunon strategy
	Study interventio	n
Serious hypersensitivity reactions	Systemic reactions to large therapeutic molecules can be IgE or non-IgE-mediated and	To mitigate the potential risk of serious hypersensitivity reactions during and after administration of
	are generally characterised by	tezepelumab, specific requirements

signs and symptoms such as skin rash, urticaria, pruritus, local or diffuse erythema, angioedema, fever, chills, cough, dyspnoea, wheezing, bronchospasm, nausea/vomiting, diaphoresis, chest pain, tachycardia or bradycardia, and/or hypotension, which can all be severe or life-threatening. Effects typically occur during or within several hours after study intervention but may be delayed.

The administration of a monoclonal antibody can result in the formation of ADA. The occurrence of ADA could result in immune complex disease (Type 3 hypersensitivity reactions) with manifestations such as serum sickness, nephritis, and vasculitis, or altered tezepelumab levels or activity.

for observing participants for AEs/SAEs and for monitoring vital signs are included in this CSP. In addition, medical equipment to treat acute anaphylactic reactions will be immediately available and site staff will be trained to recognise and treat anaphylaxis.

To mitigate the potential risk of immune complex disease participants will be monitored for confirmed immune complex disease through routine monitoring of AEs/SAEs.

Participants with sensitivity to any component of the study intervention or a history of drug or other allergy that, in the opinion of the investigator or medical monitor, contraindicates their participation will be excluded. Participants who have a history of anaphylaxis or documented immune complex disease following any biologic therapy will also be excluded.

Serious hypersensitivity reactions are an AESI and these events will be monitored closely throughout the study.

Helminth infections

Potential inhibitory effects on immune responses mediated by Th2 cells, leading to the possibility of diminution of the host's protective response to parasitic infestation/infection.

Participants with a helminth infection diagnosed within 6 months prior to Visit 1 that has not been treated with, or has failed to respond to, standard of care therapy will be excluded.

Helminth infections are an AESI. Participants who develop such infections will be monitored closely throughout the study.

Study procedures

COVID-19 Pandemic, risk of COVID-19 infection	There is the risk of exposure to COVID-19 to participants during site visits	Local guidelines will be followed to mitigate risk of participant's exposure to COVID-19.
micetion		To identify potential COVID-19 infection during the study a COVID-19-related questionnaire is recommended prior to every visit. Visits will be deferred if abnormalities noted.
		Sites are recommended to follow local severe acute respiratory coronavirus 2 (SARS-CoV-2) testing guidelines, if applicable.
		COVID-19 vaccination is allowed during the study (see Table 6). Refer to Appendix I Coronavirus (COVID 19) Pandemic Guidance.

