5. STUDY POPULATION

Prospective approval of protocol deviations to recruitment and enrolment criteria, also known as protocol waivers or exemptions, is not permitted.

Each subject should meet all the inclusion criteria and none of the exclusion criteria for this study in order to be assigned/randomized to the study intervention. Under no circumstances can there be exceptions to this rule. Subjects who do not meet the eligibility requirements are screen failures (refer to Section 5.4).

In this protocol, "enrolled" subjects are defined as those who sign the informed consent. "Randomized" subjects are defined as those who undergo randomization and receive a randomization number.

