5.2 Exclusion Criteria

Subjects should not enter the study if any of the following exclusion criteria are fulfilled:

Medical conditions:

- 1. Clinically important pulmonary disease other than COPD, as judged by Investigator, (e.g., active lung infection, main clinical feature is bronchiectasis or emphysema, pulmonary fibrosis, cystic fibrosis, hypoventilation syndrome associated with obesity, lung cancer, alpha 1 anti-trypsin deficiency and primary ciliary dyskinesia) or another diagnosed pulmonary or systemic disease that is associated with elevated peripheral eosinophil counts (e.g., allergic bronchopulmonary aspergillosis (ABPA)/mycosis, eosinophilic granulomatosis with polyangiitis (EGPA), hypereosinophilic syndrome) and/ or radiological and/or laboratory findings suggestive of a respiratory disease other than COPD that is contributing to the subject's respiratory symptoms.
- 2. Current asthma diagnosis according to the Global Initiative for Asthma (GINA) guidelines (GINA 2018) or other accepted guidelines. Patients with a history of asthma, including paediatric asthma or asthma-COPD Overlap Syndrome (ACOS), are not eligible for the study.
- 3. Any disorder, including, but not limited to, cardiovascular, gastrointestinal, hepatic, renal, neurological, musculoskeletal, infectious (including risk factors for pneumonia), endocrine, metabolic, haematological, immune, psychiatric, or major physical impairment that is not stable in the opinion of the Investigator and/or could:
 - (a) Affect the safety of the subject throughout the study
 - (b) Influence the findings of the study or their interpretation
 - (c) Impede the subject's ability to complete the entire duration of study

Note: Subjects who have epilepsy must be on a stable dose of medication for 28 days prior to randomization.

4. Unstable ischemic heart disease, arrhythmia, cardiomyopathy, heart failure, renal failure, uncontrolled hypertension as defined by the Investigator, or any other relevant cardiovascular disorder as judged by the Investigator or any ECG abnormality obtained during the screening period that in Investigator's judgement may put the patient at risk or negatively affect the outcome of the study.

- 5. Treatment with systemic corticosteroids and/or antibiotics, and/or hospitalization for a COPD exacerbation within 14 days prior to enrolment (Visit 1), based on last dose of corticosteroids or last date of hospitalization, whichever occurred later.

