 - Note: Refer to Exclusion criteria 19 for restriction with maintenance systemic steroid treatment.
- 6. History of clinically significant infection (excluding pneumonia), acute upper or lower respiratory infection, requiring antibiotics or antiviral medication within 14 days prior to enrolment (Visit 1) based on the last day of antibiotic/antiviral treatment or hospitalization date, whatever occurred later.
- 7. History of pneumonia requiring antibiotics or antiviral medication within 28 days prior to enrolment (Visit 1) or during the screening period, based on the last day of antibiotics or hospitalization date, whatever occurred later or during the enrolment and screening period.
- 8. Known history of allergy or reaction to any component of the investigational product formulation.
- 9. History of anaphylaxis to any other biologic therapy.
- 10. Donation of blood, plasma, or platelets within the past 90 days prior to Visit 1.
- 11. A helminth parasitic infection diagnosed within 24 weeks prior to Visit 1 that has not been treated with, or has failed to respond to, standard of care therapy.
- 12. History of alcohol or drug abuse within the past year, which may compromise the study data interpretation as judged by Investigator or Study Physician.
- 13. History of cancer:
 - Subjects who have had basal cell carcinoma, localized squamous cell carcinoma of the skin or in situ carcinoma of the cervix are eligible to participate in the study provided that curative therapy was completed at least 12 months prior to Visit 1.
 - Subjects who have had other malignancies are eligible provided that curative therapy was completed at least 5 years prior to Visit 1.
- 14. Subjects who in the opinion of the Investigator have evidence of active tuberculosis (TB), either treated or untreated, or latent TB without completion of an appropriate course of treatment. Evaluation will be according to the local standard of care as determined by local guidelines and may consist of medical history and physical examinations, chest x-ray, sputum stain and/or culture, and/or TB test (e.g., purified protein derivative or QuantiFeron test).
- 15. Major surgery within 8 weeks prior to Visit 1 or planned surgical procedures

requiring general anaesthesia or in-patient status for >1 day during the conduct of the study.

Prior/concomitant therapy:

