 - A serum β-HCG pregnancy test must be drawn for women of childbearing potential at the screening visit. If test result is positive, the subject should be excluded. Since urine and serum tests may miss a pregnancy in the first days after conception, relevant menstrual history and sexual history, including methods of contraception, should be considered. Any subject whose menstrual and/or sexual history suggests the possibility of early pregnancy should be excluded.
- 35. Judgment by the Investigator that the subject should not participate in the study if the subject is unlikely to comply with study procedures, restrictions and requirements or for safety reasons.

Genetic Research exclusion criteria:

- 36. Previous allogeneic bone marrow transplant.
- 37. Non-leukocyte depleted whole blood transfusion within 120 days of genetic sample collection.

COVID-19 pandemic exclusion criteria:

- 38. Judgment by the Investigator that the subject should not participate in the study based on assessment of COVID-19 symptoms for active COVID-19 infection or is febrile (≥ 38°C; ≥ 100.4°F) suspected due to COVID-19 infection.
- 39. Positive SARS-CoV-2 naso/oropharyngeal swab test, positive rapid antigen test or positive alternative test (approved by local health authorities) for active infection at Visit 1.
- 40. Chest X-ray performed during the screening period which shows abnormalities or evidence of COVID-19 pneumonia that precludes the patient's ability to complete the study.

Note: Under special circumstances, a recently done historical chest X-ray (anterior-posterior and lateral)/CT/MRI for other reasons (not study related) might be acceptable. The outcome of the X-ray/CT/MRI must be documented in the patients' medical records. Study Physician approval of historical chest X-ray must be obtained prior to randomization.

41. Receipt of any COVID-19 vaccine within 28 days prior to date of randomization.

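### Protocol Table 3 says documented immune complex disease after any biologic is excluded, but section 5.2 carries only the anaphylaxis half

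*Protocol*

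**What the plan says.** Protocol section 2.3, Table 3, lists serious hypersensitivity reactions among the potential risks. The rationale column explains the interest in immune complex disease: "The occurrence of ADA could result in immune complex disease (Type 3 hypersensitivity reactions) with manifestations such as serum sickness, nephritis, and vasculitis". The mitigation column offers two measures. One operates during the study: "participants will be monitored for confirmed immune complex disease through routine monitoring of AEs/SAEs". The other operates at entry: "Participants who have a history of anaphylaxis or documented immune complex disease following any biologic therapy will also be excluded".

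Protocol section 5 makes the numbered criteria the test for entry and allows no waivers: "Each subject should meet all the inclusion criteria and none of the exclusion criteria for this study in order to be assigned/randomized".

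Four criteria in section 5.2 come near the subject:

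- Exclusion 8: "Known history of allergy or reaction to any component of the investigational product formulation".
- Exclusion 9: "History of anaphylaxis to any other biologic therapy".
- Exclusion 3, on disorders of many kinds, includes "immune, psychiatric, or major physical impairment that is not stable in the opinion of the Investigator and/or could" affect the subject's safety, among other consequences.
- Exclusion 35 lets the investigator refuse a subject judged "unlikely to comply with study procedures, restrictions and requirements or for safety reasons".

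**The concern.** The risk section and the eligibility list describe different populations. Table 3 gives the exclusion as a rule with two limbs, anaphylaxis and immune complex disease. Section 5.2 turns only the first limb into a criterion. Screening staff work from the numbered list, so the second limb depends on an investigator recalling Table 3 or choosing to use a general clause.

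What is at stake is the safety of an individual subject. Someone with serum sickness or vasculitis after an earlier antibody could pass every named criterion and receive another monoclonal antibody. Prior antibody treatment does not bar entry: exclusion 22 asks only for a washout of 4 months or 5 half-lives, whichever is longer. The remaining safeguards are adverse event monitoring, anti-drug antibody sampling (section 8.5.2) and special-interest status for serious hypersensitivity reactions (section 8.3.8). All of these act after dosing has begun.

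**Working it through.** The plan states no figure to reproduce. The check is a comparison of texts, followed by some date arithmetic on how many randomisations the mismatch could have touched.

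**Step 1: is the history named anywhere in the criteria?** Section 5.1 runs to inclusion 20 and section 5.2 to exclusion 41. Exclusions naming immune complex disease: 0 of 41. Exclusions naming anaphylaxis to a biologic: 1 of 41 (number 9). No inclusion criterion names either.

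**Step 2: does a named criterion cover it by definition?**

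- Exclusion 9: no. Appendix G 2 defines anaphylaxis and immune complex disease under separate headings.
- Exclusion 8: no. It is limited to components of the study product's formulation.
- Exclusion 33: no. It concerns immunodeficiency, hepatitis B and hepatitis C.

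**Step 3: does a general clause require exclusion?** Exclusion 35 rests wholly on investigator judgement. Exclusion 3 lists immune disorders, but it is written for a disorder that is unstable or could cause harm or interfere with the study. A past reaction that has fully resolved may or may not be read as such a disorder. Both clauses permit exclusion, and neither clearly compels it.

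**Step 4: did Table 3 intend discretion?** The sentence just before the quoted one, on drug or other allergy, is expressly subject to the opinion of the investigator or medical monitor. The sentence on anaphylaxis and immune complex disease has no such qualifier.

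**Step 5: timing.** The version 7 summary of changes records Table 3 as new. It also records an edit to exclusion 39, so section 5.2 was open in the same amendment. Inputs:

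- Last version 7 signature: 4 November 2022 (signature page).
- Estimated last patient completed: Q1 2024, that is 1 January to 31 March 2024 (section 1.2).
- Completion: section 4.4 ties it to the last scheduled contact, which for a subject following the full schedule is Week 64 (Table 2). 64 × 7 = 448 days.

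Last randomisation = completion date − 448 days:

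- 1 January 2024 − 448 days = 10 October 2022, which is 25 days before the signature.
- 31 March 2024 − 448 days = 8 January 2023, which is 65 days after the signature.

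Appendix A 1 requires ethics committee and applicable regulatory approval before a change to the study design is implemented, so the usable period is shorter than these figures suggest. The Week 64 visit window of ±7 days is ignored here.

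**The case against.** The best defence is that the protocol already deals with the case. Exclusion 3 expressly lists immune disorders, and its second limb, concerning what could affect safety, can be read as standing apart from the investigator's opinion on stability. Table 3 is part of the same protocol and tells the investigator that this history matters. A site would have to overlook both to randomise such a subject. The risk is also ranked modestly: it sits under potential rather than important potential risks, and section 2.3 reports a low incidence of anti-drug antibodies to date. The rationale in Table 3 concerns antibodies formed against the administered product and does not quantify any added risk from a reaction to a different biologic.

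Much of this stands, and it keeps the point minor. It does not close the gap, because it makes an unqualified exclusion depend on how a general clause is read.

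A reader might infer that this is the only Table 3 exclusion without a named criterion. That is not so: a history of drug or other allergy is not named in section 5.2 either. The difference is that Table 3 leaves allergy to judgement, so a discretionary clause such as exclusion 35 is a fair counterpart to it.

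**Conclusion.** The inconsistency is real and minor. Table 3 promises an entry exclusion that the operative list only half delivers. A site following section 5.2 as written could randomise a subject whom the risk section says is excluded.

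Few or no subjects are likely to be affected. The number with this history cannot be derived from the documents. The window of about 25 days before to 65 days after signature rests on two assumptions: that the Q1 2024 estimate, entered in version 6 and carried forward, was still current, and that completion means Week 64. At the early end of that range, no randomisation took place under version 7.

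A reader might infer that ineligible subjects were enrolled, or that sites had no ground to refuse them. The documents show neither: they contain no enrolment data on this history, and exclusions 3 and 35 supply a ground for refusal. Nothing here bears on sample size, power or analysis.

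**What to change.** Extend exclusion 9 to carry both limbs, for example: *Previous anaphylaxis, or documented immune complex disease, after any biologic therapy.* If the sponsor meant to leave immune complex disease to the investigator, reword Table 3 to say so and cite exclusions 3 and 35.

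The change is one line of text, but it must go into an amendment that needs ethics committee and regulatory approval. The other cost is a few possible screen failures among people with this history.
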